Patients in the Cohort Expansion part will be treated with the RP2D from the Dose Escalation part. Patients may receive up to nine cycles of treatment. Reduced dose can be administered in accordance with the mitigation strategies (Section 8.4.4 to 8.4.5.6) or at the discretion of the treating physician based on individual patient observed toxicity profile and quality of life evaluation, and after consultation and agreement by the sponsor Medical Officer.

The specific indications for the Cohort Expansion part will be decided once the RP2D has been determined. Then, inclusion and exclusion criteria for a reduced number of previous lines of treatment will be specified for all potential indications.

[figure not shown]
At the end of the trial, Genmab will ensure provision of continued treatment to patients with clinical benefit defined as SD or better, until unacceptable toxicity or PD is observed. This will be done through a separate extension trial protocol.

Patients will be treated with up to nine cycles. The treatment period will last for up to 36 weeks (or less after changing to the once q3wk dosing scheme) or until unacceptable toxicity or disease progression at the discretion of the treating physician. The treatment duration is shortened compared to the Dose Escalation part in order to align with the treatment duration in the GEN701 trial and since patients with clinical benefit will be ensured continued treatment beyond this duration if so desired.

Severe ocular toxicity has been observed in the dose dense program 1.2 mg/kg 3q4wk and an urgent safety Protocol Amendment 4.0 has been implemented. No patients will further receive the dosing schedule 3q4wk; instead, tisotumab vedotin (HuMax-TF-ADC) 2.0 mg/kg will be administrated once q3wk on Day 1 of each 21-day cycle regardless of the prior dose(s) administered. The next dose of tisotumab vedotin cannot be administered until at least 21 days have elapsed since the last administration.

Figure 4: Dose Scheme for the Cohort Expansion Part After Urgent Safety Measurepresents the new dosing scheme according to the implementation of the urgent safety measure (Protocol Amendment 4.0):

Figure 4: Dose Scheme for the Cohort Expansion Part After Urgent Safety Measure

CE=Cohort Expansion

Nine cycles are expected to correspond to approximately 27 weeks.

Final 5.0 (incorporating Protocol Amendment 4) 06 Jul 2017

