¹⁶ For patients with ovarian and endometrial cancer.

¹⁷ Flow cytometry only on Cycle 1 and Cycle 5.

¹⁸ HBsAg, anti-HBs and anti-HBc, Hepatitis C and antibodies to CMV antigen will be assessed at screening for all patients; for CMV, anti-IgG and IgM will be assessed and, in case of positive IgM, it will be confirmed with CMV PCR; for HCV, anti-IgG will be assessed and, if positive, it will be confirmed with HCV PCR. HPV only for patients with cervical cancer. At EOT, only antibodies to CMV antigen will be assessed.

¹⁹ See Table 4 and Section 10.17 for details of PK samplings.

²⁰ Archived biopsy material can be forwarded if a sample is available. If no sample is available, a new tumor biopsy must be obtained at least 2 weeks before dosing to ensure healing of wound.

²¹ Only on Cycle 4.

²² Preventive eye therapy to be administered in relation to infusions as detailed in Section 8.4.5.3.

Table 4: PK Sampling - Cohort Expansion Part - SUPERSEDED

Treatment Cycle	Screening			Cycle 1				Cycle 2-9		Unscheduled
Visit Number	0	1	2	3	4	5	1	2	3	1-X
Day/Week	-	1d	8d	15d	18d	22d	1d	8d	15d	
Before Infusion (on infusion days)	X	X	X	X	X	X	X	X	X	X^2
End of infusion (+15 minutes) ¹		X					X			
+ 2 hours (± 15 minutes) after end of infusion ¹		X								

¹ Allowed time windows are indicated in parentheses.

² Optional.

 Table 5:
 Trial Flow Chart – Cohort Expansion Part - After Urgent Safety Measure

Treatment Cycle	Screening		Cycle 1			Cycle 2-9	1	EOT ¹	Withdrawal Safety Follow-up ²	Unscheduled
Visit Number	0	13	2	3	1 ³	2	3	-	-	1-X
Day/Week	≤ 21 days prior to Visit C1-V1	1d	8d	15d	1d	8d	15d	-	30 days after last dosing	-
Visit window ⁴		-	±1d	±1d	±3d	±1d	±1d	-	±14d	-
Informed Consent	X ⁵									
Eligibility Criteria	X									
Demographics	X									
Medical History ⁶	X									
Height and Body Weight ⁷	X	X			X			X		
Physical Examination	X	X						X		
Vital Signs ⁸	X	X	X	X	X		X	X		X^9
ECG ¹⁰	X	X			X			X		X^9
CT-Scan	X ¹¹				X^{12}			X^{12}		X^9
ECOG Performance Status	X	X			X			X		X ⁹
Adverse Events	X	X	X	X	X		X	X	X	X ⁹
Concomitant Medication	X	X	X	X	X		X	X		X^9
Trial Drug Administration ²²		X			X					
Bleeding Assessment	X	X		X	X			X		X
Skin Assessment	X	X		X	X			X		X
Neuropathy Assessment	X	X		X	X			X		X
Ophthalmological Evaluation	X			X^{13}			X^{13}	X ¹³		X^{13}
Radionuclide Bone Scan ¹⁴	X				X					X^9
LABORATORY ASSESSMENT	Γ S ¹⁵									
Hematology	X	X	X	X	X	X	X	X		X^9
Biochemistry	X	X	X	X	X	X	X	X		X^9
Coagulation factors	X	X	X	X	X	X	X	X		X^9

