Treatment Cycle	Screening		Cycle 1			Cycle 2-9		EOT ¹	Withdrawal Safety Follow-up ²	Unscheduled
Visit Number	0	1^3	2	3	13	2	3	-	-	1-X
Day/Week	≤21 days prior to Visit C1-V1	1d	8d	15d	1d	8d	15d	-	30 days after last dosing	-
Visit window ⁴		-	±1d	±1d	±3d	±1d	±1d	-	±14d	-
PSA ¹⁴	X	X			X			X		X^{10}
CA 125 ¹⁶	X	X			X			X		X ¹⁰
Flow Cytometry		X^{17}			X ¹⁷			X		X^{10}
Pregnancy Test	X	X			X			X		X^{10}
ADA (Immunogenicity)	X	X			X					X^{10}
Hepatitis B, C, CMV, HPV ¹⁸	X							X		X^{10}
PK Sampling ¹⁹	X	X	X	X	X	X	X			X^{10}
Tumor biopsy	X^{20}									X^{10}
Biomarker	X						X^{21}			

Abbreviations: ADA=anti-drug antibody; CMV=cytomegalovirus; CRPC=Castration-resistant prostate cancer; CT=computerized tomography; ECG=electrocardiogram; ECOG=Eastern Cooperative Oncology Group; EOT=End of Trial; HBc=Hepatitis B core; HBs=Hepatitis B surface; HBsAg=Hepatitis B surface antigen; HCV=hepatitis C virus; HPV= human papilloma virus; Ig=Immunoglobulin; PCR=polymerase chain reaction; PD=progressive disease; PK=pharmacokinetic; PSA=prostate specific antigen; SAE=serious adverse event

Footnotes to Trial Flowchart: Cohort Expansion Part

¹ If the patient shows PD, is to start new anti-cancer treatment or withdraws from trial due to another reason during treatment, the EOT Visit should be performed as soon as possible after decision of withdrawal.

²Only SAEs will be assessed.

³ The patient shall stay at hospital for at least 2 hours after the infusion and may be requested to stay longer at the discretion of the investigator.

⁴ The specified visit windows are in accordance with the previous visit. Visit 1 of Cycle 2 and onwards should be performed 7 days ± 3 days after Day 15 of the previous cycle.

⁵ Informed consent must be obtained before or at the Screening Visit window i.e., may be reasonably prior to the screening date.

⁶ Signs and symptoms occurring between Visit 0 and first infusion should be recorded as medical history (see Section 10 for details). SAEs should be reported as of the signing of the informed consent.

⁷ Height is only assessed at the Screening Visit. During the trial, only body weight is measured on the first dosing day in a cycle, as part of the dose calculation. If body weight is assessed \leq 7days before the first day of the planned dosing in a cycle, this value can be used to calculate dose.

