8.4.1 Treatments Administered

The investigator must ensure that the trial drug will be used only in accordance with the protocol.

Tisotumab vedotin (HuMax-TF-ADC) will be administered as an intravenous infusion on Days 1, 8 and 15 of each cycle (one treatment cycle is 28 days).

After implementation of the urgent safety measure (Protocol Amendment 4), tisotumab vedotin (HuMax-TF-ADC) 2.0 mg/kg will be administrated once q3wk on Day 1 (one treatment cycle is 21 days), regardless of the prior dose(s) administered. The next dose of tisotumab vedotin (HuMax-TF-ADC) cannot be administered until at least 21 days have elapsed since the last administration.

Each patient's dose will be calculated based on the patient's weight rounded to the nearest kilogram, i.e., assigned cohort dose in mg/kg × body weight in kg. The weight used per cycle should be the weight taken in connection with the first dosing visit of the current cycle (see Section 10.3). For patients whose body mass index (BMI) is greater than 30 kg/m², the investigator should use a weight that, based on the patient's height, corresponds to a maximum BMI of 30.

The dose is calculated according to the following formula if BMI is greater than 30kg/m²:

Dose
$$(mg) = x (mg/kg) * 30 (kg/m2) * height (m) * height (m)$$

Final 5.0 (incorporating Protocol Amendment 4) 06 Jul 2017

Tisotumab vedotin (HuMax-TF-ADC) will be administered over a minimum of 30 minutes. If infusion-related events emerge, refer to Section 8.4.4. The infusion is complete when the infusion line has been flushed with a minimum 15 mL saline. Preventive eye therapy should be administered in relation to infusions as detailed in Section 8.4.5.3.

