- CTCAE grade 2 conjunctivitis: Hold dosing. Topical treatment should be initiated by the ophthalmologist (according to treatment guidelines below). When the event has improved to ≤ CTCAE grade 1, dosing of trial drug can be resumed at a reduced dose (please refer to dose modification scheme below).
 - o In case of recurrence of conjunctivitis CTCAE grade 2 the patient should hold dosing and topical treatment should be initiated by the ophthalmologist (according to treatment guidelines below). When the event is CTCAE grade ≤ 1, dosing of trial

Final 5.0 (incorporating Protocol Amendment 4)
06 Jul 2017

drug can be resumed at a further reduced dose (please refer to dose modification scheme below).

- If the conjunctivitis recurs again at CTCAE grade 2, the patient should hold dosing and topical treatment should be initiated by the ophthalmologist (according to treatment guidelines below). When the event is CTCAE grade ≤ 1, dosing of trial drug should not be further reduced but resumed at 0.9 mg/kg.
- CTCAE grade ≥ 3 conjunctivitis: Hold dosing. Topical treatment should be initiated by the ophthalmologist (according to treatment guidelines below). When the event has improved to CTCAE grade ≤ 1, dosing of trial drug can be resumed at a reduced dose (please refer to dose modification scheme below).
 - o If the conjunctivitis recurs at CTCAE grade ≥ 3 , the patient must permanently discontinue treatment with trial drug.

Keratitis:

Grading: All events of keratitis should be graded according to both:

- Ophthalmological grading based on the objective eye-examination findings performed by the ophthalmologist.
- CTCAE grading system based on NCI-CTCAE criteria assessed by the investigator (CTCAE version 4.03).

Dose delay and dose modification:

- CTCAE grade ≤ 2 keratitis: Hold dosing until the event is managed effectively by topical treatment (according to treatment guidelines below) initiated by the ophthalmologist. When the event is ≤ CTCAE grade 1, dosing of trial drug can be resumed at a reduced dose (please refer to dose modification scheme below).
 - o In case of recurrence of CTCAE grade ≤ 2 keratitis, the patient should hold dosing and topical treatment (according to treatment guidelines below) should be initiated by the ophthalmologist. When the event is CTCAE grade ≤ 1 , dosing of trial drug can be resumed at a further reduced dose (please refer to dose modification scheme below).

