 - In case of 3^{rd} occurrence of keratitis CTCAE grade ≤ 2 , the patient must permanently discontinue treatment with trial drug.
- CTCAE grade ≥ 3 keratitis: The patient must permanently discontinue treatment with trial drug.

Final 5.0 (incorporating Protocol Amendment 4) 06 Jul 2017

Conjunctival ulceration:

If an ophthalmological evaluation reveals fluorescent patches or conjunctival ulceration of any grade:

- Hold dose until conjunctivitis/conjunctival ulceration is managed effectively by topical treatment (according to treatment guidelines below). When the event is managed effectively, dosing of trial drug can be resumed at a reduced dose (please refer to dose modification scheme below).
- o If symptoms do not stabilize/improve after dose reduction, the patient must permanently discontinue treatment with trial drug.

Treatment guidelines

_	
Ocular symptom	Treatment guideline (The length of treatment should be decided by the local ophthalmologist)
Conjunctivitis: CTCAE grade 1	The local ophthalmologist should prescribe frequent dosing of preservative-free topical steroid drops
Conjunctivitis: CTCAE grade 2	The local ophthalmologist should prescribe frequent dosing (every 2nd hour) of preservative-free topical steroid drops in conjunction with preservative free antibiotic prophylaxis such as chloramphenicol
Conjunctivitis: CTCAE grade 3	The local ophthalmologist should prescribe frequent dosing (every 2nd hour) of preservative-free topical steroid drops in conjunction with preservative free antibiotic prophylaxis such as chloramphenicol
Keratitis: CTCAE grade 1	The local ophthalmologist should prescribe frequent dosing of preservative-free topical steroid drops
Keratitis: CTCAE grade 2	The local ophthalmologist should prescribe frequent dosing (every 2nd hour) of preservative-free topical steroid drops in conjunction with preservative free antibiotic prophylaxis such as chloramphenicol
Conjunctival ulceration: any grade	The local ophthalmologist should prescribe frequent dosing (every 2nd hour) of preservative-free topical steroid drops in conjunction with preservative free antibiotic prophylaxis such as chloramphenicol

Final 5.0 (incorporating Protocol Amendment 4)
06 Jul 2017

Dose modification scheme:

Previous dose of tisotumab vedotin	Reduced dose of tisotumab vedotin	
2.0 mg/kg	1.3 mg/kg	
1.3 mg/kg	0.9 mg/kg	
0.9 mg/kg	0.9 mg/kg*	

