9 TRIAL EVALUATIONS

Trial evaluations by visit are detailed in the Schedules of trial procedures in Table 1 and Table 3 according to the initially designed treatment scheme. Trial evaluations by visit for the Cohort Expansion part after implementation of the urgent safety measure (Protocol Amendment 4.0) are detailed in Table 5. A description of the methods of assessments is provided in Section 10.

All patients who are assigned a patient number and receive any trial drug will be followed according to the protocol regardless of the number of doses received, unless consent is withdrawn. The investigator must notify the sponsor or designee of deviations from protocol visits or evaluations, and these evaluations, if applicable, must be rescheduled or performed at the nearest possible time to the original schedule. Protocol deviations will be recorded on the source document with an explanation for the deviations and any trial-specific eCRF or logs designated for capturing protocol deviations, if applicable for the trial. The investigator must comply with the applicable requirements related to the reporting of protocol deviations to the IEC/IRB.

Patients will be instructed to call the trial personnel to report any abnormalities during the intervals between trial visits and to come to the trial site if medical evaluation is needed and the urgency of the situation permits. For emergency and other unscheduled visits to a medical facility other than the trial site, medical records will be obtained by the investigator and made available to the sponsor or designee during monitoring visits.

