10 METHODS OF ASSESSMENT

Trial procedures will be performed on the trial dates noted in Table 1 and Table 3 according to the initially designed treatment scheme, and in Table 5 after implementation of the urgent safety measure (Protocol Amendment 4.0). A description of the different assessments is provided below.

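### Grade ≤ 2 keratitis ends treatment at the third occurrence in one rule but at the third recurrence (the fourth occurrence) in two lists; secondarily, the Table 5 dosing-visit window omits the 21-day minimum

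*Protocol*

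**What the plan says.** **Keratitis.** Section 8.4.5.3 sets out grade ≤ 2 keratitis step by step. At the first event dosing is held and resumed at a reduced dose. The next step opens with "In case of recurrence of CTCAE grade" ≤ 2 and ends in a further reduction. The last step covers the 3rd "occurrence of keratitis CTCAE grade" ≤ 2 and requires permanent discontinuation. The dose scheme in the same section goes from 2.0 to 1.3 to 0.9 mg/kg and no lower. The list of discontinuation criteria that closes Section 8.4.5.3, and the withdrawal list in Section 8.3.4.1, instead give the *third recurrence* of grade ≤ 2 keratitis as the trigger. The 8.3.4.1 item refers the reader to 8.4.5.3.

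**Dosing visit.** Table 5, the flow chart for the Cohort Expansion part after the urgent safety measure, marks "Trial Drug Administration" at Visit 1 of Cycles 2–9. Its footnote 4 counts each window from the previous visit and states: "Visit 1 of Cycle 2 and onwards should be performed 7 days ± 3 days after Day 15 of the previous cycle". Day 8 and Day 15 each carry ±1 day. Section 8.1 states: "The next dose of tisotumab vedotin cannot be administered until at least 21 days have elapsed since the last administration". Section 8.1.1.2 says the same, and Section 8.4.1 repeats that the next dose "cannot be administered until at least 21 days have elapsed since the last administration". Section 9 tells sites: "Trial evaluations by visit for the Cohort Expansion part after implementation of the urgent safety measure (Protocol Amendment 4.0) are detailed in Table 5". Section 10 likewise places trial procedures on the dates in Table 1 and Table 3, "and in Table 5 after implementation of the urgent safety measure (Protocol Amendment 4.0").

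**The concern.** The once-every-three-weeks schedule was adopted because severe ocular toxicity was seen at 1.2 mg/kg three times every four weeks. An ocular stopping rule and a minimum dosing interval are therefore two rules that should read the same wherever a site meets them.

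The keratitis rule does not. A site working from either list could treat a third episode as not yet a reason to stop, while a site working from the stepwise text would stop. Patients with the same history could be handled differently, and the reported treatment exposure and ocular events would then partly reflect which page was consulted.

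The dosing window is a lesser matter. A site booking visits from Table 5 alone can schedule a dosing visit on a day when the dose may not be given.

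**Working it through.** **1. Keratitis: occurrences against recurrences.** The first event is not a recurrence, so recurrence *k* is occurrence *k* + 1. The protocol uses the words this way. The stepwise text calls the second event a recurrence, and the lists use first occurrence (grade ≥ 3 keratitis) and first recurrence (grade ≥ 3 conjunctivitis) as different triggers. For a patient starting at 2.0 mg/kg with no other reductions:

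| Grade ≤ 2 keratitis episode | Stepwise text, 8.4.5.3 | Lists in 8.4.5.3 and 8.3.4.1 |
|---|---|---|
| 1st | hold, resume at 1.3 mg/kg | no stop listed |
| 2nd (1st recurrence) | hold, resume at 0.9 mg/kg | no stop listed |
| 3rd (2nd recurrence) | permanent discontinuation | no stop listed |
| 4th (3rd recurrence) | not reached | permanent discontinuation |

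The difference is one episode. Two features of Section 8.4.5.3 favour the third occurrence as the intended rule: there are exactly two reduction steps, and the step that lets a patient with a third grade 2 conjunctivitis episode resume at 0.9 mg/kg has no counterpart for keratitis.

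**2. Dosing interval: the plan's own figure.** On the nominal schedule the interval is 7 + 7 + 7 = 21 days, and nine cycles take 9 × 21 / 7 = 27 weeks. This agrees with the approximately 27 weeks given in Section 8.1.

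**3. Footnote 4 with Day 15 on time.** The interval since the last dose is 14 + 7 + *c* days, with *c* from −3 to +3, giving 18 to 24 days. Days 18, 19 and 20, 3 of the 7, fall below 21.

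**4. Footnote 4 with windows counted from the previous visit.** The interval is (7 + *a*) + (7 + *b*) + (7 + *c*) = 21 + *a* + *b* + *c*, with *a* and *b* from −1 to +1 (Day 8, Day 15) and *c* from −3 to +3. That is 3 × 3 × 7 = 63 combinations.

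| *a* + *b* | Ways | Interval (days) | Values below 21 | Values of 21 or more |
|---|---|---|---|---|
| −2 | 1 | 16–22 | 5 | 2 |
| −1 | 2 | 17–23 | 4 | 3 |
| 0 | 3 | 18–24 | 3 | 4 |
| +1 | 2 | 19–25 | 2 | 5 |
| +2 | 1 | 20–26 | 1 | 6 |

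Below 21: 1×5 + 2×4 + 3×3 + 2×2 + 1×1 = 27. At 21 or more: 1×2 + 2×3 + 3×4 + 2×5 + 1×6 = 36. These are counts of combinations, not probabilities.

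**5. Possible repairs to the window.**
- *Add a floor of 21 days since the last infusion.* This keeps exactly the 36 compliant combinations, with 2 to 6 usable days in every case.
- *Re-anchor to the last infusion, 21 days +3.* The interval becomes 21–24 days. This removes intervals above 24 that are now allowed: *a* + *b* = +1 with *c* = +3 (2 combinations, day 25) and *a* + *b* = +2 with *c* = +2 or +3 (2 combinations, days 25 and 26). Four compliant combinations are lost.
- *Use −0/+3 days from Day 15.* Four combinations still fall short, at 19 or 20 days (2 with *a* + *b* = −2 and 2 with *a* + *b* = −1). Four compliant ones are lost, three at day 21 and one at day 22.

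Only the floor removes every short interval and keeps every permitted one.

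**The case against.** On keratitis, the stepwise text is mandatory at the third occurrence and offers no way to resume. Each list item is a sufficient reason to stop, not a licence to continue, so a reader who infers that the lists authorise re-dosing after a third episode goes further than the text. Other protections also stand: any keratitis leads to a dosing hold, grade ≥ 3 keratitis stops treatment at once, dose modifications should be preapproved by the sponsor Medical Officer (Section 8.4.5), and non-serious grade 2 ocular events are reported within 24 hours (Section 11.4.2.1).

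All of this limits the risk, but none of it says which count applies. The 24-hour rule for non-serious grade 2 ocular events does not reach grade 1. The reference from 8.3.4.1 leads to a section that contains both versions. The separate rule on more than two dose reductions need not trigger at a third episode either, because a patient already at 0.9 mg/kg is not reduced further.

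On the window, a reader might infer that the protocol allows dosing at 16 to 20 days. It does not. The footnote says when a visit should take place; the 21-day rule is an outright prohibition, stated three times, and both can always be met together. Sections 9 and 10 refer to Table 5 for evaluations and procedures, while the dosing instruction in 8.4.1 carries the minimum. This objection largely succeeds: what remains is a missing cross-reference in a chart that also marks drug administration.

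**Conclusion.** The keratitis discrepancy is a true contradiction in an ocular stopping rule. It amounts to one episode of grade ≤ 2 keratitis, normally in a patient already reduced to 0.9 mg/kg. The conclusion rests on reading recurrence as the protocol itself uses it. That the third occurrence was intended is a well-supported inference from the reduction steps, and the clinical team should confirm it. The document does not show whether Amendment 4 introduced the wording, so no cause is assigned.

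The dosing window is secondary. Footnote 4 shows 3 of 7 days below the minimum with visits on time, and 27 of 63 combinations when windows chain, all of them already barred. The number of early doses that the protocol permits is zero.

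**What to change.** Keratitis: replace *third recurrence* with *third occurrence* of grade ≤ 2 keratitis in Section 8.3.4.1 and in the discontinuation list of Section 8.4.5.3, after confirmation by the sponsor's clinical team.

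Dosing visit: keep the ±3-day window and add to Table 5 footnote 4 *and in no case earlier than 21 days after the last infusion*. Do not re-anchor the window to 21 days +3, which would remove days 25–26 now permitted after late visits, and do not use −0/+3 from Day 15, which still shows 19 or 20 days after early visits.

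The cost is two list items, one footnote clause and a clarification letter to sites. Sample size, endpoints and assessments are unaffected.
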